7.2.4 Assessment of Causality

The investigator’s assessment of causality must be provided for all AEs (serious and non-serious). An investigator’s causality assessment is the determination of whether there exists a reasonable possibility that the investigational product caused or contributed to an AE. Causality of an AE will be assessed by the investigator using the following terms:

- **Likely Related:** A reaction that follows a reasonable temporal sequence from administration of the study drug; that follows a known or expected response pattern to the suspected study drug; and for which other potential etiologies are considered less likely factors than the study drug.
- **Likely Unrelated:** A reaction that, considering all potential etiologies, is most likely due to factors other than the study drug.

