7.3 Follow-up of Adverse Events and Serious Adverse Events

The investigator must make every effort to follow all AEs and SAEs regardless of attribution until judged resolved or stabilized, the subject is lost to follow-up, or it has been determined that study drug treatment or participation in the study is not the cause of the AE or SAE.

7.4 Reporting Serious Adverse Events to the Sponsor and Institutional Review Board or Ethics Committee

The Sponsor or designee is under obligation to report certain SAEs to regulatory authorities related to investigational drugs in clinical trials. The Sponsor or designee must be notified within 24 hours of an AE when the investigator determines that an AE meets the protocol definition of an SAE, regardless of the cause or relationship to study drug.

An SAE related to study participation occurring before study drug administration and after informed consent should be promptly reported to the Sponsor. If the investigator learns of any SAE at any time after a participant has been discharged from the study, and the SAE is considered likely related to study drug, the SAE should be promptly reported to the Sponsor.

Please see the Safety Form Report Completion Instructions for safety reporting instructions.

The investigator must also comply with applicable requirements concerning reporting of SAEs to the IRB or Ethics Committee (EC). This may include initial or follow-up notification of an SAE or other safety information.

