7.5 Reporting Serious Adverse Events to Regulatory Authorities and Study Investigators

The Sponsor, or its designee, is responsible for submitting reports of serious, unexpected related adverse events to regulatory authorities on an expedited basis, according to the ICH E2A Guideline and to other regulatory authorities according to national and local regulations as required. The Sponsor, or its designee, is responsible for prompt submission to the IRB or EC of any expedited SAE reports submitted to regulatory authorities. All investigators participating in ongoing clinical studies with serlopitant will receive copies of the SAE reports submitted on an expedited basis to regulatory authorities.

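### The Likely Related definition in Protocol 7.2.4 is narrower than the section's own causality standard, so novel or equally attributable AEs fit neither of the two compulsory terms

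*Protocol*

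**What the plan says.** Protocol Section 7.2.4 requires a causality rating for every AE, serious or not. It states the question as "whether there exists a reasonable possibility that the investigational product caused or contributed to an AE" and then offers two terms and no third.

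- *Likely Related* has three parts, joined by *and*. The first is timing: "A reaction that follows a reasonable temporal sequence from administration of the study drug". The second is pattern: the event must be one "that follows a known or expected response pattern to the suspected study drug". The third is ranking: every competing explanation must be judged less probable than the drug.
- *Likely Unrelated* is "A reaction that, considering all potential etiologies, is most likely due to factors other than the study drug".

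SAP Section 2.3.7.1 repeats the reasonable-possibility question and names the same two terms. It does not define them and sends the reader to the protocol for detail.

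The rating is used in several places. Protocol 8.9.1 and SAP 3.5.1 tabulate treatment-related events. For an SAE that the investigator learns of after the subject has left the study, Section 7.4 says that if "the SAE is considered likely related to study drug, the SAE should be promptly reported to the Sponsor". Section 7.5 makes the sponsor "responsible for submitting reports of serious, unexpected related adverse events to regulatory authorities on an expedited basis".

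**The concern.** The general question and the definition of Likely Related set different thresholds. The question is met if the drug plausibly caused the event or contributed to it. The definition adds two demands: the reaction must already belong to a recognised pattern for the drug, and the drug must outrank every other explanation. A first occurrence of a true drug effect can meet the question and fail the definition.

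The two terms also leave a gap between them. An investigator who must choose one, for an event that fits neither, has no rule to follow, and about 40 sites may settle the matter differently.

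At stake are the treatment-related TEAE summaries, for which the documents describe no second causality assessment of non-serious events, and possibly the reporting of SAEs that come to light after discharge. The wording also sits awkwardly beside an expedited-report category whose purpose is to capture events that are both related and unexpected.

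**Working it through.** No arithmetic applies, and the plan gives no figure to reproduce. The check compares the two definitions with the stated standard.

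**Are the three conditions joint?** Yes. The list in Section 7.2.4 ends in *and*. The note that a semicolon means *or* belongs to Table 1 and is limited to the grade descriptions there, so it does not turn the causality conditions into alternatives.

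**Which events fit which term?** Suppose the timing fits and there is one competing cause. Two features then matter: whether the pattern is already known for the drug, and how the drug ranks against the other cause.

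| Pattern known? | Drug against other cause | Likely Related? | Likely Unrelated? | Literal result |
|---|---|---|---|---|
| Yes | Drug more likely | Yes | No | Likely Related |
| No | Drug more likely | No (pattern) | No | Neither |
| Yes | Equal | No (ranking) | No | Neither |
| No | Equal | No (both) | No | Neither |
| Yes | Other more likely | No | Yes | Likely Unrelated |
| No | Other more likely | No | Yes | Likely Unrelated |

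Three of the six combinations have no term. These are logical cases, not frequencies. In all three the drug is at least as likely a cause as the alternative, so the reasonable-possibility question would naturally be answered yes.

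In the last two rows the terms do give an answer, but it can contradict the standard. An event due mainly to something else, to which the drug plausibly contributed, meets the stated question and is still labelled Likely Unrelated.

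**Does the SAP repair this?** No. SAP 2.3.7.1 carries the broader standard without the pattern condition, but it refers back to the protocol for the meaning of the terms.

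**Where does the label lead?**

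- Treatment-related AE tables (Protocol 8.9.1, SAP 3.5.1): directly dependent on it.
- SAEs learned of after discharge (Protocol 7.4): the trigger uses the same words as the label, though in lower case and without citing 7.2.4. Section 7.2.1 puts the condition for reports after the follow-up visit more broadly, as a belief that the drug was responsible. The two sentences do not match.
- On-study SAEs (Protocol 7.4): not dependent on it. The sponsor must be notified within 24 hours whatever the cause.
- Expedited reports (Protocol 7.5): a dependence on the label is not stated. The section neither cites 7.2.4 nor says whose judgement of relatedness decides.

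**The case against.** The strongest reply is that investigators are given a sound standard in the same section, and again in the SAP, and can apply it. On that view there are two inconsistent instructions and no prohibition. That is fair, and it is why the point is a contradiction to be reconciled and not a bar on calling a new reaction related. It does not remove the problem, because the definitions attached to the actual response options are the narrower ones.

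The second reply is that the main safeguards do not use the label. All TEAEs, serious TEAEs, severity grades and discontinuations due to TEAEs are summarised by arm whatever their attribution. In a 1:1 placebo-controlled trial, those comparisons can reveal a novel reaction. Every on-study SAE reaches the sponsor. This stands, and it limits the severity. It does not protect the treatment-related tables or the post-discharge sentence in Section 7.4.

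A reader might go further and infer that no event can be both unexpected and related, so that the expedited category in Section 7.5 is empty. That would need two premises which the documents do not supply: that *related* there means only the investigator's Likely Related label, and that *unexpected* is the exact opposite of a known or expected pattern. The protocol does not define *unexpected*, and Section 7.5 places the duty on the sponsor under ICH E2A and national rules. An event of a known type but of unexpected severity might still qualify, though this is an assumption about the term.

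A reader might also try to scale the loss from the treatment-related rates quoted for TCP-102 in Protocol 1.3.3. The documents do not give that study's causality definitions, so those rates cannot serve as a yardstick.

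Finally, the eCRF guidance and the safety-form instructions are not among the documents and may already clarify the matter. That cannot be checked here, and it would not excuse conflicting protocol text.

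**Conclusion.** The contradiction within Section 7.2.4 is real and can be seen from that section alone. Read literally, novel reactions with the drug as the likeliest cause, and events with evenly balanced causes, have no applicable term, although one must be chosen. Events to which the drug only contributed can be labelled contrary to the stated standard.

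The consequences are possible misclassification in the treatment-related TEAE tables and possible non-reporting of a novel SAE learned of after discharge. The number of events cannot be estimated from the documents. It depends on how often such events occur and on whether investigators follow the definition or the general question. The efficacy analyses, all-cause safety tables and on-study SAE notification are unaffected, and the inference that Section 7.5 covers nothing is not supported. This is an inconsistency that should be fixed, not one that undermines the trial.

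**What to change.** Reconcile the definitions in Protocol 7.2.4 with the standard that the section already states, so that the two terms cover every event. Related would mean that there is a reasonable possibility that study drug caused or contributed to the event. Unrelated would mean that there is no such possibility. Response pattern, timing and alternative causes can remain as considerations that inform the judgement, but not as conditions that must all be met.

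Align the post-discharge sentence in Section 7.4 with the revised wording and with Section 7.2.1, and carry the same text into the eCRF guidance. SAP 2.3.7.1 already has the reasonable-possibility standard and contains no pattern condition to remove; if the terms are renamed, only the names need to follow.

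The cost is a short wording change with no new data collection. The downside is that somewhat more AEs will be rated related, in both arms. The change is best made before ratings accumulate, since re-rating later would rest on retrospective judgement.

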7.3 Follow-up of Adverse Events and Serious Adverse Events

The investigator must make every effort to follow all AEs and SAEs regardless of attribution until judged resolved or stabilized, the subject is lost to follow-up, or it has been determined that study drug treatment or participation in the study is not the cause of the AE or SAE.

7.4 Reporting Serious Adverse Events to the Sponsor and Institutional Review Board or Ethics Committee

The Sponsor or designee is under obligation to report certain SAEs to regulatory authorities related to investigational drugs in clinical trials. The Sponsor or designee must be notified within 24 hours of an AE when the investigator determines that an AE meets the protocol definition of an SAE, regardless of the cause or relationship to study drug.

An SAE related to study participation occurring before study drug administration and after informed consent should be promptly reported to the Sponsor. If the investigator learns of any SAE at any time after a participant has been discharged from the study, and the SAE is considered likely related to study drug, the SAE should be promptly reported to the Sponsor.

Please see the Safety Form Report Completion Instructions for safety reporting instructions.

The investigator must also comply with applicable requirements concerning reporting of SAEs to the IRB or Ethics Committee (EC). This may include initial or follow-up notification of an SAE or other safety information.

7.5 Reporting Serious Adverse Events to Regulatory Authorities and Study Investigators

The Sponsor, or its designee, is responsible for submitting reports of serious, unexpected related adverse events to regulatory authorities on an expedited basis, according to the ICH E2A Guideline and to other regulatory authorities according to national and local regulations as required. The Sponsor, or its designee, is responsible for prompt submission to the IRB or EC of any expedited SAE reports submitted to regulatory authorities. All investigators participating in ongoing clinical studies with serlopitant will receive copies of the SAE reports submitted on an expedited basis to regulatory authorities.

7.6 Emergency Unblinding

The investigator will immediately notify the Sponsor or the medical monitor to discuss the need for unblinding any subject via IWRS. There is no specific antidote for serlopitant and usual supportive medical management is recommended in the case of a medical emergency.

8 STATISTICAL METHODS

Endpoints will be summarized with descriptive statistics by treatment group and visit/timepoint. For continuous variables, the following information will be presented: n (number of subjects), mean, standard deviation, median, minimum and maximum. For categorical variables counts and percentages will be used. Summary statistics for imputed efficacy data will be reported based upon imputed data.

Baseline for measures other than the eDiary daily measures will be the last recorded value prior to the start of treatment. For daily measures including the WI-NRS, baseline will be the average result measured over the week prior to treatment.

A statistical analysis plan (SAP), describing all statistical analyses will be provided as a separate document. The SAP will be finalized prior to unblinding of the study treatments.

8.1 Decision Rule and Sample Size

This study will use a 5% one-sided alpha level.

The target sample size of 200 randomized and dosed subjects (100 per group) has been determined based upon a 1:1 allocation of subjects to treatment groups and a 5% one-alpha level. A sample size of two hundred subjects results in at least 90% power assuming a placebo Week 10 4-point responder rate of █% and serlopitant 4-point responder rate of █%.

The sample size calculations have been performed in PASS 13 ([“PASS 13 Power Analysis and Sample Size Software” 2014](#)) and use a Chi-Squared test. The primary analysis will control for the stratification factors. It is expected that this unstratified power estimate will under-estimate the true power as it does not take the variance reduction resulting from stratification into account ([Matts 1988](#)).

8.2 Handling of Missing Data

Should a determination of treatment period (on treatment, pre-treatment, follow-up) be required for adverse events or concomitant medication but the corresponding date is missing, or is a partial date, the event/medication will be considered on treatment unless the portions of the date that are available indicate this is not possible.

If a subject fails to complete their eDiary for a week or more, the WI-NRS endpoints, including the primary endpoint, may be missing. In this case, the WI-NRS change from baseline value will be imputed. The approach uses the subject's last week with data. From that point forward their trajectory will be imputed based upon the trajectory of their treatment group.

The imputation approach first determines the average change for each week for each treatment group. The difference in the weekly measures between weeks n-1 and n will be considered the change for Week n. Any missing changes will be imputed to produce and them combined with the prior known value to produce a change from baseline result. For

example, a placebo subject with known results at Week 4 but missing at Week 6 will have their Week 6 WI-NRS change from baseline imputed as $\Delta_4 + \Delta_{P(4-6)}$, where Δ_4 is the observed change from baseline result for the subject up to Week 4 and $\Delta_{P(4-6)}$ is the average placebo change from Week 4 to 6 (i.e. the average placebo decrease from Week 4 to 6).

For the responder endpoints, the same imputation will be performed and the responder status determined based upon the change from baseline and the subject's disposition and rescue medication status (See [Section 8.8](#)).

As a sensitivity analysis, a similar approach will be used where the imputation step uses multiple imputation methodology.

8.3 Analysis Populations

The primary efficacy population will be the full analysis population (FAP) and will include all randomized subjects who were dispensed study drug. Subjects will be analyzed within the treatment group to which they are randomized.

The primary safety population will be all treated subjects. For safety analyses, subjects will be classified based upon the treatment received.

8.4 Subject Disposition

An accounting of all randomized subjects by disposition will be presented. Subjects who discontinue study drug prematurely or withdraw from the study will be summarized and listed, with a description of the reason for early termination/withdrawal.

8.5 Subject Characteristics

Demographic and other baseline characteristics will be summarized.

8.6 Prior and Concomitant Medications

Prior and concomitant medications will be coded by the World Health Organization Drug Dictionary to Anatomical Therapeutic Classification (ATC) and preferred drug name.

Prior therapies (including over-the-counter medications) used to treat pruritus within the prior 3 months will be reported. Prior medications will be summarized by ATC level and preferred drug name and listed.

Concomitant medications will be summarized by ATC level and preferred drug name and listed. Concomitant medication use will be quantified and analyzed.

8.7 Treatment Compliance and Extent of Exposure

Compliance with study drug dosing will be determined based on tablet counts recorded on the eCRF. Compliance will be calculated by analyzing expected number of tablets returned versus actual number of tablets returned. Summaries of treatment exposure will also be produced.

8.8 Efficacy Analyses

All efficacy endpoints will be summarized within the FAP using descriptive statistics by time point and treatment.

8.8.1 *WI-NRS*

Subject record their WI-NRS measurements daily in an electronic diary. These daily measures are combined into weekly measures (Baseline, Weeks 2, 4, 6, 8, 10, Follow-up) by averaging the daily measurements. Change from baseline is the difference between baseline and the post baseline weeks. Missing data will be imputed as outlined in [Section 8.2](#). From this change from baseline the binary responder status (responder / non-responder) is created. A subject is a 4-point responder if their change from baseline is ≤ -4 (i.e. a decrease of at least 4). A 3-point responder is similarly defined. Subjects who withdraw from the study due to a lack of efficacy or require rescue therapy for treatment of worsening pruritus within four weeks prior to the timepoint will be defined as non-responders regardless of their change from baseline.

The daily WI-NRS endpoint (change from baseline in daily WI-NRS scores through Week 2) is the change between the baseline WI-NRS (same baseline as the weekly measures) and the daily measures over the first two weeks.

8.8.2 *Primary Efficacy*

The WI-NRS 4-point responder rate at Week 10 (primary endpoint) will be summarized by treatment group. The difference in responder rates between treatment arms will be tested using a CMH test controlling for the ‘as randomized’ stratification factors. Conceptually the hypotheses being tested are:

$$H_0: P_{Placebo} \geq P_{serlopitant} \quad H_a: P_{Placebo} < P_{serlopitant}$$

where $P_{Placebo}$ is the percent of placebo responders and $P_{serlopitant}$ is the similar percent for serlopitant.

Sensitivity analyses using other missing data rules will be performed.

8.8.3 *Secondary Efficacy and Exploratory*

Secondary endpoints will be summarized with descriptive statistics by time point and treatment. These summary measures will include baseline, result at the time point and change from baseline as is appropriate for the endpoint. Missing data imputation will be limited to the WI-NRS and WI-VAS endpoints.

The differences between treatment groups for the WI-NRS 4-point at Weeks 2, 4, 6, and 8, and 3-point responder rates at Weeks 2, 4, 6, 8, and 10 will be tested using the CMH test identical to the one used for the primary endpoint.

The change from baseline to Weeks 2, 4, 6, 8, and 10 and Days 1–14 for the WI-NRS will be testing using an analysis of variance (ANOVA) model with treatment group and stratification factor as fixed effects. The change in WI-VAS to Weeks 2, 4, 6, and 10 will be tested using a similar ANOVA model.

8.9 Safety Analyses

8.9.1 Adverse Events

The incidence of all AEs and treatment-related AEs will be tabulated by treatment received. These AEs will be classified by system organ class and preferred term using the Medical Dictionary for Regulatory Activities (MedDRA). For incidence reporting, if a subject reported more than one AE that was coded to the same system organ class or preferred term, the subject will be counted only once for that specific system organ class or preferred term. An overview of AEs, which includes subject incidence of AEs, treatment-related AEs, AEs by severity, SAEs, deaths, and AEs leading to discontinuation, will be presented.

SAEs will be listed and summarized in a similar manner to AEs.

8.9.2 Clinical Safety Laboratory Results

Clinical safety laboratory values will be measured by a central laboratory. Summary statistics for actual values and for changes from baseline will be tabulated for laboratory results by scheduled visit. Graphs of laboratory values over time will also be produced.

Subjects with clinical laboratory values outside of the normal reference range at any post-baseline assessment will be summarized. Shifts from baseline laboratory values will be tabulated.

8.9.3 Vital Signs

The observed data and change from baseline for each measurement day will be summarized with descriptive statistics.

8.9.4 Electrocardiograms

The overall ECG assessment (abnormal or normal) will be summarized and descriptively characterized, along with a summary of how many subjects developed a post treatment abnormal result.

